7.3 RECORDS RETENTION17

8 STUDY FINANCES 18

8.1 FUNDING SOURCE 18
8.2 CONFLICT OF INTEREST 18
8.3 SUBJECT STIPENDS OR PAYMENTS 18
8.4 REGULATORY INFORMATION 18
9 REFERENCES 19

LIST OF ABBREVIATIONS

AE	Adverse Event/Adverse Experience
HIPAA	Health Insurance Portability and Accountability Act
PTT	Penile traction therapy
PD	Peyronie's Disease
RCT	Randomized controlled trial

Study Summary

Title	Penile Lengthening Maintenance Post-prostatectomy
IRB Protocol Number	18-001013
Methodology	Controlled randomized study
Overall Study Duration	3 years
Subject Participation Duration	9 months
Objectives	Evaluate the efficacy of the RestoreX penile traction device in preventing loss of penile length in men undergoing prostatectomy
Number of Subjects	90
Diagnosis and Main Inclusion Criteria	Men undergoing prostatectomy
Study Device	RestoreX®, penile traction therapy
Duration of Exposure	Subjects will use device for 5 months for: 30 minutes, once daily, 5 days a week OR 30 minutes, twice daily, 7 days a week After the randomized period, all subjects will be entered into an open-label phase where they may choose to use or not use the device for 3 additional months
Reference therapy	During the randomized phase, the use of the device will be compared against a control group using no traction therapy In the open label phase, results at the end of 9 months will be compared to those from baseline and at the beginning of the open label phase
Statistical Methodology	Stratification of subjects prior to randomization to assure an equal representation based on baseline penile length. Statistical comparisons will be made comparing total penile length prior to and following therapy. Comparisons of subjective questionnaire responses will also be made between groups and at the various time points captured.

1 Introduction

This document is a protocol for a human research device study. This study will be carried out in accordance with the procedures described in this protocol, applicable United States government regulations and Mayo Clinic policies and procedures.

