3.5 Study Schema

Prior to surgery, data will be recorded by the surgeon using the current standard of care questionnaires (EPIC-50, IIEF-15 disease specific variables, and demographics).

Following surgery, patients will be seen in the clinic based on the standard routine clinical practice for their catheter removal (approximately 1-3 weeks post-prostatectomy). At this time, and after the patient has consented, they will undergo initial study penile length assessments (described later in the protocol) and be educated on how to use the device properly by a trained nurse. Patients will then be given a baseline questionnaire to complete. In some cases, patients may not have been provided the IIEF-15 questionnaire prior to surgery. For these patients that have not yet filled out this questionnaire and had their data recorded in their records, they will instead receive the IIEF-15 questionnaire during this baseline visit.

Once consent and study assessments are completed, the patients will be randomized into one of three groups:

1. PTT for 30 min 1x/day, 5 days/week
2. PTT for 30 min 2x/day, 7 days/week
3. Control (no treatment)

Patients in the treatment arm will record a daily journal of their usage of the device. Patients will then begin using the device 4 weeks after surgery as instructed for the times appropriate to their group. This ensures adequate time for the patient to recover from their procedure before beginning to use the device. The study coordinator will call the patient to remind them to begin using the device.

After 5 months of using the device (+1.5 months permitted), patients will return for subsequent assessments (see below) and a follow-up questionnaire. At this time, patients will be encouraged to report any adverse events. They will also be requested to bring their device back to the clinic to review proper usage and any questions on the device. After completion of the subsequent assessments, patients will begin a 3-month, open-label phase of the trial. During this period, the patients will be allowed to use the device for 30 minutes at a time, with a frequency to be determined by the patient.

After completion of the 3-month open-phase portion of the trial, patients will return to the clinic to undergo final assessments, which are identical to the 6-month assessments. Patients will then be encouraged to self-report any additional adverse events (AE's) that they encounter over the subsequent 6 months.

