5.2 Statistical Analysis

Analyses will be performed using comparisons within patients of same baseline penile stretch length and between groupings of varying lengths. Comparison of penile length between traction and no traction will be made, as well as reviewing historical records to increase statistical power. Comparison of length from baseline to post-traction for individual participants will also be reviewed.

The data will also be analyzed in three ways: 1- with all patients included, regardless of their compliance to utilize the device for the recommended treatment time, 2- with patients excluded if they failed to achieve 90% compliance with the recommended duration of treatment, 3- with patients excluded if they failed to achieve 80% compliance with the recommended duration of treatment.

Comparisons will also be made on other subjective and objective variables obtained including number of adverse events, complications, subjective responses to questionnaires, or

other information. All data will be normalized based on pre-operative stretched penile length.

6 Safety and Adverse Events

Definition of Adverse Event

Unanticipated Problems Involving Risk to Subjects or Others (UPIRTSO) - any unanticipated problem or adverse event that meets the following three criteria:

Serious: Serious problems or events that results in significant harm, (which may be physical, psychological, financial, social, economic, or legal) or increased risk for the subject or others (including individuals who are not research subjects). These include: (1) death; (2) life threatening adverse experience; (3) hospitalization - inpatient, new, or prolonged; (4) disability/incapacity - persistent or significant; (5) breach of confidentiality and (6) other problems, events, or new information (i.e. publications, interim findings, product labeling change) that in the opinion of the local investigator may adversely affect the rights, safety, or welfare of the subjects or others, or substantially compromise the research data, AND

Unanticipated: (i.e. unexpected) problems or events are those that are not already described as potential risks in the protocol, consent document, not listed in the Investigator's Brochure, or not part of an underlying disease. A problem or event is "unanticipated" when it was unforeseeable at the time of its occurrence. A problem or event is "unanticipated" when it occurs at an increased frequency or at an increased severity than expected, AND

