Related: A problem or event is "related" if it is possibly related to the research procedures.

Adverse Event - an untoward or undesirable experience associated with the use of a medical product (i.e. drug, device, biologic) in a patient or research subject.

Serious Adverse Event - adverse events are classified as serious or non-serious. Serious problems/events can be well defined and include:

- Death
- Life threatening adverse experience
- Hospitalization
- Inpatient, new, or prolonged; disability/incapacity
- And/or per protocol may be problems/events that in the opinion of the sponsor-investigator may have adversely affected the rights, safety, or welfare of the subjects or others, or substantially compromised the research data.

All AEs that do not meet any of the criteria for serious, should be regarded as non-serious AEs.

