6.5 Recording of Adverse Events

The study team will seek information on adverse events by specific questioning between baseline and the followup visits. Information on all adverse events will be recorded immediately in the adverse event section of the specific questionnaire as well as in an adverse event form (see Attachment – Adverse Event Form).

All adverse events occurring during the study period will be recorded. The clinical course will be followed until resolution, stabilization, or until it has been ultimately determined that the study treatment or participation is not the probable cause. Serious adverse events that are still ongoing at the end of the study period will be followed up, to determine the final outcome. Any serious adverse event that occurs after the study period and is considered to be at least possibly related to the study treatment or study participation will be recorded and reported immediately.

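### The adverse-event definition is tied to use of a medical product while controls receive no study product, so a traction-versus-control comparison of adverse-event numbers would not be like for like

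*Combined protocol and SAP*

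**What the plan says.** - **Definition (section 6).** An AE is "an untoward or undesirable experience associated with the use of a medical product", where the product may be a drug, device or biologic. Association with a product is part of the definition itself.
- **Control arm (Study Summary; section 3.5).** In the randomised phase "the use of the device will be compared against a control group using no traction therapy". Section 3.5 lists the third arm as an untreated control.
- **Planned comparison (section 5.2).** "Comparisons will also be made on other subjective and objective variables obtained including number of adverse events". Complications and questionnaire responses are listed alongside. No groups, time window or test are given.
- **Recording (section 6.5).** "All adverse events occurring during the study period will be recorded". The team asks about events at follow-up, with no restriction by arm.
- **Pre-existing conditions and new findings (section 6.2).** A pre-existing condition that worsens is an AE, with no product-use condition. New findings at the end of the study are recorded only if they meet the AE definition.
- **Relatedness (section 6.6.1).** The AE form has a separate item for relationship to the study.
- **Follow-up period (section 6.1).** It runs 3 months from the last study treatment.
- **After the randomised phase (Study Summary).** "all subjects will be entered into an open-label phase where they may choose to use or not use the device".

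**The concern.** Every participant has just had a prostatectomy, so pain, swelling, infection and voiding problems can occur in any arm with no contribution from the device. The untreated controls are the only concurrent source of that background. Secondary objective 3, to evaluate AEs with the device, needs it in order to tell device effects from ordinary recovery.

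If product association decides what counts as an event, the control arm may under-report by rule. Ordinary post-operative events could then look like device harm, or a real excess could be dismissed because no credible comparator exists. Section 6 gives staff no instruction on how to classify an untoward event in a control.

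**Working it through.** **1. The sections side by side.** The documents give no AE rate, significance level or test for this comparison, so there is no planned figure to reproduce. The first check is textual.

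| Section | Does it require product association? |
|---|---|
| 6, definition | Yes |
| 6.2, worsened pre-existing condition | No |
| 6.2, new findings | Yes, by referring back to the definition |
| 6.5, recording | Questioning is not limited by arm, but what is recorded is an AE as defined |
| 6.6.1, relationship item | Treats association as something judged after recording |
| 6.1, follow-up period | Anchored to study treatment; a control who never uses the device has no anchor date |

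The sections do not agree on whether association is a condition for recording or an attribute judged afterwards.

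**2. What the comparison measures under each reading of 'associated'.**
- *Temporal* (the event occurred while a product was in use). A post-operative event in a traction man qualifies. The same event in a control qualifies only if he was using some other product, or if it is a worsened pre-existing condition.
- *Causal* (the product brought the event about). Background events drop out of every arm. What remains is essentially product-related events, and controls give no background rate.
- *Ignored* (staff record everything in all arms). The comparison is like for like, but only because the definition was not followed.

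**3. Worst-case size under the temporal reading.** Inputs: 30 men per arm (section 3.4), hence 2 × 30 = 60 traction and 30 control. Assumptions, none of them in the documents: a background proportion p with at least one event, equal in all arms; no device effect; no control event counted; two-sided Fisher exact test at 0.05.

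At the expected count 60p in traction men against 0/30:

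| p | Traction | Control as counted | Fisher p |
|---|---|---|---|
| 10% | 6/60 | 0/30 | 0.173 |
| 20% | 12/60 | 0/30 | 0.0071 |
| 30% | 18/60 | 0/30 | 0.00044 |

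Against 0/30, the smallest traction count with a Fisher p below 0.05 is 8 (7/60 gives 0.090; 8/60 gives 0.048). The chance of a false signal is therefore P(X ≥ 8) with X ~ Binomial(60, p). The comparator sums the joint binomial probabilities over all tables with a Fisher p below 0.05, in either direction, when both arms are counted by the same rule.

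| p | Control events not counted | Same rule in both arms |
|---|---|---|
| 5% | 1.0% | 2.3% |
| 10% | 24.8% | 3.1% |
| 20% | 93.3% | 3.6% |
| 30% | 99.9% | 3.7% |

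For one traction arm against control (30 v 30), the threshold against 0/30 is 6 events. The uncounted-control figures are 0.3%, 7.3%, 57.2% and 92.3%, against 0.1%, 0.9%, 2.2% and 2.6% under the same rule.

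**The case against.** A reader might infer that controls cannot have an AE at all, so that the comparison is one-sided by construction. The documents do not support that. The definition covers any drug, device or biologic, so a control using another product can qualify, and section 6.2 admits worsened pre-existing conditions without any product. Section 6.5 does not limit questioning by arm, follows events until treatment or participation is ruled out as the cause, and so suggests recording before causality is settled. The 6-month questionnaire is scheduled without an arm split, whereas the randomised-phase diary goes only to treated men. The AE form and questionnaires are attachments outside the available text and may already put the same questions to every arm.

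Other points also stand:
- Section 5.2 does not name the groups. The comparison could be between the two traction regimens, and objective 3 says evaluate, not compare. Traction versus no traction is the natural reading, because it is the contrast section 5.2 names for length, but it is not stated for AEs.
- Section 5.2 lists complications separately, and these might capture some post-operative events in controls.
- The illustration reads 'associated' loosely enough to count every background event in traction men and strictly enough to exclude every control event. On a causal reading the false signal largely disappears.
- A reader might also infer a planned count to 9 months by randomised arm, with device use mixed into the controls. No section plans one, and the Study Summary compares open-label results with baseline and with the start of that phase. What remains is that section 5.2 sets no AE window to rule such a count out.

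These points narrow the claim but do not remove it. Section 6.5 and the new-findings rule in 6.2 both lead back to the product-linked definition, and no visible text says how a control's event is classified. The causal reading removes the false signal only by giving up the background rate.

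**Conclusion.** The concern holds in a limited form. The AE definition makes product association a condition for counting, one arm has no study product in the randomised phase, and sections 6.2, 6.5 and 6.6.1 pull in different directions. A traction-versus-control comparison under section 5.2 is then either asymmetric (temporal reading) or restricted to product-related events (causal reading). In neither case do controls reliably supply a background rate.

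The size cannot be established from the documents. The false-signal chances of 1.0% to 99.9% are a worst case. They rest on assumed background rates of 5% to 30%, the temporal reading, no control event counted, and a test and threshold that the plan does not specify. They show that the wording could matter a great deal at plausible rates, not that a false signal will occur. The point affects one secondary objective and the AE comparison, not the primary length outcome. It should be corrected because the ambiguity is real and the correction is cheap.

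**What to change.** - **Section 6.** Define an AE as any untoward medical occurrence in a participant from randomisation onward, in any arm, whether or not associated with the device. Keep relatedness as the separate AE-form item in section 6.6.1, so that device-related events can still be reported on their own. Bring the wording of sections 6.1 and 6.2 into line, including a follow-up anchor that exists for a man who never uses the device.
- **Section 5.2.** Name the groups compared. Base the between-arm comparison on events from randomisation to the 6-month visit, by randomised arm, with the same questions in all three arms.
- **Open-label phase.** Tabulate these events separately, because controls may then use the device. The diaries given to all participants at 6 months allow a split by actual use.

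The cost is a short wording change, more non-device events on AE forms (mainly in controls), and a higher total AE count. Because serious AEs are a subset of AEs, the sponsor should also check that the wider definition and the study-halt count in section 6.6.2 still agree with each other.

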6.1 Adverse Event Reporting Period

For the current study, the treatment follow-up period is defined as 3 months following the last administration of study treatment.

6.2 Preexisting Condition

A preexisting condition is one that is present at the start of the study. A preexisting condition should be recorded as an adverse event if the frequency, intensity, or the character of the condition worsens during the study period.

At screening, any clinically significant abnormality should be recorded as a preexisting condition. At the end of the study, any new clinically significant findings/abnormalities that meet the definition of an adverse event must also be recorded and documented as an adverse event.

6.3 Post-study Adverse Event

All unresolved AEs will be followed by the study team until the events are resolved, the subject is lost to follow-up, or the AE is otherwise explained. A review of AEs which the subject or subject's physician believe might reasonably be related to participation in the study will be performed up to 9 months following surgery.

6.4 Hospitalization, Prolonged Hospitalization or Surgery

Any AE related to the study intervention that results in hospitalization or surgery should be documented and reported as a serious AE.

Neither the condition, hospitalization, prolonged hospitalization, nor surgery are reported as an adverse event in the following circumstances:

- Hospitalization or prolonged hospitalization for diagnostic or elective surgical procedures for a preexisting condition. Surgery should not be reported as an outcome of an adverse event if the purpose of the surgery was elective or diagnostic and the outcome was uneventful.

6.5 Recording of Adverse Events

The study team will seek information on adverse events by specific questioning between baseline and the followup visits. Information on all adverse events will be recorded immediately in the adverse event section of the specific questionnaire as well as in an adverse event form (see Attachment – Adverse Event Form).

All adverse events occurring during the study period will be recorded. The clinical course will be followed until resolution, stabilization, or until it has been ultimately determined that the study treatment or participation is not the probable cause. Serious adverse events that are still ongoing at the end of the study period will be followed up, to determine the final outcome. Any serious adverse event that occurs after the study period and is considered to be at least possibly related to the study treatment or study participation will be recorded and reported immediately.

6.6 Reporting of Serious Adverse Events and Unanticipated Problems

When an adverse event has been identified, the study team will take appropriated action necessary to protect the study participant and then complete the Adverse Event Form. The sponsor-investigator will evaluate the event and determine the necessary follow-up and reporting required.

6.6.1 Sponsor-investigator Reporting: Notifying the Mayo IRB

An adverse event form will be completed for any serious adverse event. This will be reported to the Mayo IRB in a de-identified manner.

The study team will report to the Mayo IRB any UPIRTSOs and Non-UPIRTSOs according to the Mayo IRB Policy and Procedures.

Information collected on the adverse event form (and entered into the research database)

- Subject's ID
- Description of adverse event
- The date the adverse event occurred and resolved (if applicable)
- Intensity
- Outcome
- Action taken to address
- Relationship to study
- Impact on study withdrawal
- Classification as serious or not

The sponsor-investigator will review all adverse event reports to determine if specific reports need to be made to the IRB. The sponsor-investigator will sign and date the adverse event report when it is reviewed. For this protocol, only directly related SAEs/UPIRTSOs will be reported to the IRB.

6.6.2 Stopping Rules

Any serious adverse event which is determined to reasonably be related to the study device by the sponsor-investigator will result in immediate discontinuation of the therapy. If 5

patients develop serious adverse events, the study will be halted with re-review required by the Mayo IRB prior to consideration of study resumption.

6.6.3 Medical Monitoring

Medical monitoring of serious adverse events will be performed by the study investigator on a monthly-basis if serious adverse events have been reported.

7 Data Handling and Record Keeping

7.1 Confidentiality

Information about study subjects will be kept confidential and managed according to the requirements of the Health Insurance Portability and Accountability Act of 1996 (HIPAA). Those regulations require a signed subject authorization informing the subject of the following:

- What protected health information (PHI) will be collected from subjects in this study
- Who will have access to that information and why
- Who will use or disclose that information
- The rights of a research subject to revoke their authorization for use of their PHI.

In the event that a subject revokes authorization to collect or use PHI, the investigator, by regulation, retains the ability to use all information collected prior to the revocation of subject authorization. For subjects that have revoked authorization to collect or use PHI, attempts should be made to obtain permission to collect at least vital status (long term survival status that the subject is alive) at the end of their scheduled study period.

7.2 Source Documents

Source data comprise all information, original records of clinical findings, observations, or other activities in a clinical trial necessary for the reconstruction and evaluation of the trial. Source data are contained in source documents. Examples of these original documents, and data records include: hospital records, clinical and office charts, laboratory notes, memoranda, subjects' diaries or evaluation checklists, pharmacy dispensing records, recorded data from automated instruments, copies or transcriptions certified after verification as being accurate and complete, microfiches, photographic negatives, microfilm or magnetic media, x-rays, subject files, and records kept at the pharmacy, at the laboratories, and at medico-technical departments involved in the clinical trial. When applicable, information recorded on the CRF shall match the Source Data recorded on the Source Documents.

